1.0 Background

Lotriga Granular Capsules (the “Drug”) is an oral capsule formulation containing the active ingredient omega-3 fatty acid ethyl esters (principally EPA-E and DHA-E). The Drug differs from general marine oil products, such as supplements, in containing a high concentration of omega-3 fatty acid ethyl esters. Since first approved in Norway in September 1994, the Drug has been in extensive use overseas, sold in more than 60 countries. In the clinical study of the Drug conducted in Japan in patients with hypertriglyceridemia, adverse drug reactions (ADRs) including ‘laboratory test abnormal’ were observed in 91 (9.6%) of the 948 patients administered at 2 g or 4 g of omega-3 fatty acid ethyl esters, and the major ADR was Diarrhea (2.5%).

Despite the proven track record of extensive use overseas and the fact that the safety of long-term use was already evaluated during the clinical study, it is important to evaluate the safety of long-term use of the Drug in the general patient population in Japan.

Special drug use surveillance (hereinafter the "Study") has been therefore designed to evaluate the safety and efficacy of long-term use of the Drug in patients with hyperlipidemia in a routine clinical setting.

2.0 Objective

To evaluate the safety and efficacy of long-term use of the Drug in patients with hyperlipidemia in a routine clinical setting.

3.0 Target Sample Size and Rationale for Sample Size Setting

3.1 Target Sample Size

3,000 patients

3.2 Rationale for Sample Size Setting

Bleeding-related events are set as a priority survey item for the Drug. As postmarketing surveillance of EPA products in antihyperlipidemic therapy has reported that the incidence of bleeding-related ADRs was 0.4% and that the percentage of anticoagulant and antiplatelet concomitant use was about 10%, the Study sets a target of 3,000 patients so that anticoagulant and antiplatelet concomitant use can be assessed to some degree, in addition to bleeding-related ADRs.

Note that this rationale for the sample size is not based on statistical evidence.

4.0 Study Population

Patients with hyperlipidemia will be eligible for this study; however, those who meet the following exclusion criteria were excluded from the study.

Exclusion criteria:

- (1) Patients with hemorrhage (e.g., hemophilia, capillary fragility, gastrointestinal ulcer, urinary tract hemorrhage, hemoptysis, or vitreous hemorrhage)
- (2) Patients with a history of hypersensitivity to ingredients in the Drug

5.0 Dosage and Administration for Study Population

The usual adult dosage is 2 g of omega-3 fatty acid ethyl esters administered orally once daily after meals. However, the dosage can be increased up to twice daily (at a dose of 2 g) depending on the patient's triglyceride level.

6.0 Number of Study Sites by Clinical Department

About 200 sites (clinical departments not specified)

7.0 Study Method

7.1 Observation Period

12 months

7.2 Request and Contract to Study Sites

The Study will be requested and contracted using a web-based electronic data collection system [REDACTED]. Takeda Pharmaceutical's staffs (hereinafter "Takeda staffs") will adequately explain to investigators about the purpose and description of the Study, [REDACTED]'s operating procedure, electronic signature, and user ID and password handling for request for the Study, based on the Letter of Request for Cooperation in Special Drug Use Surveillance, the Implementation Guidance, data input screen images, and the abbreviated [REDACTED] Operating Manual. Takeda MRs will then conclude a contract in writing with study sites to perform the Study within the specified surveillance period.

7.3 Patient Enrollment Method

Patients will be "centrally" enrolled using [REDACTED]. The investigator will enter into [REDACTED] patient enrollment information (see Section 9.1) of patients for whom the Drug has been prescribed since the start date of the period of contract with the study site, within 14 days after the prescription date of the Drug (the prescription date is defined as "Day 0"; the day following the prescription date is defined as "Day 1").

7.4 Data Entry and Electronic Signature to Electronic Case Report Form (eCRF)

The investigator will enter patient data including demographics and treatment into [REDACTED] and electronically sign the eCRF in 12 months after the start of treatment with the Drug (baseline).

If a patient discontinues the treatment with the Drug for some reason during the observation period, the investigator will be expected to enter their information including demographics and treatment into [REDACTED] and electronically sign the eCRF within one month after the completion of necessary observations. However, if the patient discontinues the treatment with the Drug due to the occurrence of an adverse event (AE), the investigator should continue to observe them after discontinuation, as long as possible until the AE is resolved or resolving. The investigator should then enter the result of the observation into [REDACTED] and

electronically sign the eCRF.

After review of the information, Takeda Pharmaceutical may request for re-survey, if deemed necessary, via **CCI** [REDACTED]. The investigator will, upon checking, perform the details of the requested re-survey and enter the result of the re-survey into **CCI** [REDACTED] and electronically sign the eCRF.

7.5 Action Taken at Onset of Serious Adverse Event

The investigator will immediately contact the Takeda staff if a serious AE occurs during the observation period. The investigator will also separately provide detailed information thereof upon request, if any, from the Takeda staff.

8.0 Expected Duration of Study

Surveillance period: May 2013 to May 31, 2017

Patient enrollment period: May 2013 to May 31, 2015*

*Enrollment may be closed before the end of the enrollment period if the total number of patients enrolled in the Study reaches the target sample size.

9.0 Survey Items

The investigator will enter the information of the following items into **CCI** [REDACTED]. The schedule for the Study is provided in the Appendix.

9.1 Patient Enrollment

1) Survey items

Prescription date of the Date, patient ID number, patient initials, sex, birth date, determination with inclusion criteria, and determination with exclusion criteria

2) Survey timing

The time of patient enrollment

9.2 Patient Demographics

1) Survey items

Height, weight, time of hyperlipidemia diagnosis, treatment category, menopausal status (only for female), complications (presence or absence and details), medical history (presence or absence and details), hypersensitivity disposition (presence or absence and details), drinking history, smoking history, presence or absence of surgery within one month before baseline, and presence or absence of healthier lifestyle education (diet and exercise therapies)

2) Survey time

Baseline

9.3 Treatment Information

1) Survey items

Administration of the Drug (daily dose, treatment duration, and status of completion of treatment with the Drug), administration of antihyperlipidemic drugs other than the Drug* (presence or absence, drug name, daily dose, and treatment duration), and administration of concomitant medications (other than antihyperlipidemic drugs) (presence or absence, drug name, and purpose of administration)

*: Including antihyperlipidemic drugs with which treatment is discontinued within two months before baseline.

2) Survey timing

Period from baseline to Month 12 (or discontinuation of treatment)

9.4 Testing/Observation Items

1) Survey items

Triglyceride (TG), total cholesterol (TC), LDL cholesterol* (LDL-C), HDL cholesterol (HDL-C), VLDL cholesterol (VLDL-C), Apo-AI, Apo-B, Apo-CIII, lipoprotein (a), remnant lipoprotein cholesterol (RLP-C), fasting blood glucose (FBG), HbA1c

*: When tested by direct measurement

2) Survey timing

Baseline, Month 3, Month 6, Month 9, and Month 12 (or discontinuation of treatment) test timepoints

9.5 Other Observation Items

1) Survey items

Pregnancy status

If the patient is found to be pregnant during the observation period, the investigator will report the Takeda staff. The investigator will, upon request from the Takeda staff, use a sheet for pregnant women to provide detailed information (including information available up to childbirth, including premature birth or other pregnancy results, if possible).

2) Survey timing

Period from baseline to Month 12 (or discontinuation of treatment)

9.6 Adverse Events (AEs)

1) Survey items

Presence or absence of AE (see Table 1), AE name, date of onset, seriousness and reason for seriousness (see Table 2), action taken to the Drug, date of determination of outcome, outcome, and causal relationship to the Drug* (see Table 3)

If the outcome is not resolved or unknown and the causal relationship is determined as unevaluable, follow-up survey should be conducted to some extent possible.

*If causal relationship to the Drug is determined as not related, reasons that may constitute the rationale for determination should be collected if it is unevaluable.

2) Survey timing

Period from baseline to Month 12 (or discontinuation of treatment)

3) Priority survey item

Bleeding-related events occurring after baseline are set as a priority survey item. If any bleeding-related event is reported as an AE, laboratory test values related to bleeding should be separately collected.

Table 1 Definition of Adverse Event

An adverse event (AE) is any untoward medical occurrence in a patient administered a medicinal product and which does not necessarily have to have a causal relationship with this treatment.
 
An AE can therefore be any unfavorable and unintended sign (including an abnormal laboratory finding, for example), symptom, or disease temporally associated with the use of a medicinal product, whether or not considered related to the medicinal product.
 
The following should be also handled as an AE:
 
• A symptom or other problem occurring in an infant breastfed from a mother taking the medicinal product• A symptom or other problem occurring in a child administered the medicinal product• A symptom or other problem occurring in a patient administered or taking more than the approved dose of the medicinal product
--

Table 2 Seriousness Criteria


An event is classified as serious if:
 
1. resulting in death (death),2. being life-threatening (at risk of death),3. requiring inpatient hospitalization or prolongation of existing hospitalization (hospitalization/prolonged hospitalization),4. resulting in persistent or significant disability/incapacity (disorder),5. being a congenital anomaly/birth defect (birth defect), or6. being any other medically serious condition that does not fall under any of 1 to 5 above. Note that all those listed in the Takeda Medically Significant AE List are included in this criterion. (Examples include bronchospasm, which requires short-term intensive care in emergency room settings.)

Takeda Medically Significant AE List

• Acute respiratory failure/acute respiratory distress syndrome (ARDS)	• Anaphylactic shock
• Torsade de pointes/ventricular fibrillation/ventricular tachycardia	• Acute renal failure
• Malignant hypertension	• Pulmonary hypertension
• Convulsive seizure (including spasm and epilepsy)	• Pulmonary fibrosis (including interstitial lung disease)
• Agranulocytosis	• Neuroleptic malignant syndrome/malignant hyperthermia
• Aplastic anaemia	• Spontaneous abortion/stillbirth and foetal death
• Toxic epidermal necrolysis/muco-cutaneo-ocular syndrome (Stevens-Johnson syndrome)	• Confirmed or suspected transmission of infection by a medicinal product
• Hepatic necrosis	• Confirmed or suspected endotoxin shock
• Acute hepatic failure	

Table 3 Criteria for Casual Relationship between Adverse Event and the Drug

Determination	Criteria
Related	There is temporal correlation between the Drug and the event (including results from discontinuation of treatment). Or the event is an AE considered likely to have been caused by the Drug although it is presumed to have been contributed by other factors, such as primary disease, complications, concomitant medications, or combined treatments.
Not related	There is no temporal correlation between the Drug and the event. Or the event is adequately considered to have been contributed by other factors, such as primary disease, complications, concomitant medications, or combined treatments.
Unevaluable	There is lack of information necessary for evaluation of the event, including temporal correlation (including results from discontinuation of treatment), primary disease, complications, concomitant medications, and combined treatments.

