6. being any other medically serious condition that does not fall under any of 1 to 5 above. Note that all those listed in the Takeda Medically Significant AE List are included in this criterion. (Examples include bronchospasm, which requires short-term intensive care in emergency room settings.)

Takeda Medically Significant AE List

• Acute respiratory failure/acute respiratory distress syndrome (ARDS)	• Anaphylactic shock
• Torsade de pointes/ventricular fibrillation/ventricular tachycardia	• Acute renal failure
• Malignant hypertension	• Pulmonary hypertension
• Convulsive seizure (including spasm and epilepsy)	• Pulmonary fibrosis (including interstitial lung disease)
• Agranulocytosis	• Neuroleptic malignant syndrome/malignant hyperthermia
• Aplastic anaemia	• Spontaneous abortion/stillbirth and foetal death
• Toxic epidermal necrolysis/muco-cutaneo-ocular syndrome (Stevens-Johnson syndrome)	• Confirmed or suspected transmission of infection by a medicinal product
• Hepatic necrosis	• Confirmed or suspected endotoxin shock
• Acute hepatic failure	

Table 3 Criteria for Casual Relationship between Adverse Event and the Drug

Determination	Criteria
Related (if the Drug is suspected to have contributed to the event)	There is temporally evident correlation between the Drug and the event (including results from discontinuation of treatment). Or the event is an AE considered likely to have been caused by the Drug although it is presumed to have been contributed by other factors, such as primary disease, complications, concomitant medications, or combined treatments.
Not related (if the Drug is considered unlikely to have contributed to the event)	There is no temporally evident correlation between the Drug and the event. Or the event is adequately considered to have been contributed by other factors, such as primary disease, complications, concomitant medications, or combined treatments.
Unevaluable	There is lack of information necessary for evaluation of the event, including temporal correlation (including results from discontinuation of treatment), primary disease, complications, concomitant medications, and combined treatments.

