1.0 Definitions of Terms

1.1 Definitions

Item	Definition
Survey unit period (periodic safety report)	Periodic Safety Report 1: July 22, 2012 to January 21, 2013 Periodic Safety Report 2: January 22, 2013 to July 21, 2013 Periodic Safety Report 3: July 22, 2013 to January 21, 2014 Periodic Safety Report 4: January 22, 2014 to July 21, 2014 Periodic Safety Report 5: July 22, 2014 to July 21, 2015 Periodic Safety Report 6: July 22, 2015 to July 21, 2016 Periodic Safety Report 7: July 22, 2016 to July 21, 2017 Periodic Safety Report 8: July 22, 2017 to July 21, 2018
Drug	Lotriga Granular Capsules
SOC	System organ class of MedDRA.
HLGT	High level group term of MedDRA.
PT	Preferred term of MedDRA.
LLT	Lowest level term of MedDRA.
Enrolled patient	A patient approved for enrollment in the Study.
Patient with eCRF collected	An enrolled patient whose eCRF was submitted via CCI .
Patient with eCRF uncollected	An enrolled patient other than a patient with eCRF collected.
Locked patient	A patient who has completed the approval process in the PMS system.
Unlocked patient	A patient with eCRF collected other than a locked patient.
Safety-evaluable patient	A locked patient included in safety evaluation.
Safety-unevaluable patient	A locked patient excluded from safety evaluation.
Efficacy-evaluable patient	A safety-evaluable patient included in efficacy evaluation.
Efficacy-unevaluable patient	A safety-evaluable patient excluded from efficacy evaluation.
ADR	An abbreviated form of the term ‘adverse drug reaction or infection.’ Refers to an adverse event other than those judged by the investigator as ‘not related’ in causality to the Drug. In this plan, ‘adverse drug reactions or infections’ is used in headings, and ‘ADRs’ is used in the text and tables.
Serious adverse event (SAE)	[Prior-approval data] An adverse event (AE) judged as ‘serious’ by the trial investigator. [Surveillance data] An adverse event (AE) judged as ‘serious’ by the investigator. Note that events listed in the separate MedDRA code list of the Takeda Medically Significant AE List should be treated as serious even if judged as

Item	Definition
	'not serious' by the investigator.
Bleeding-related event	An event falling under Standardized MedDRA Query (SMQ) code 20000038 (hemorrhagic SMQ [narrow scope]).

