2.4.18 Onset Status of Adverse Drug Reactions or Infections by Presence or Absence of Cerebrovascular Complications

Statistical Analysis Set	Safety-evaluable patients in this special drug use surveillance
Details of Statistical Analysis	Compile ADR types by presence or absence of cerebrovascular complications. The compilation method of ADR types is the same as described in section 2.4.1.
Figure/Table No.	Table 2.4.18

2.4.19 Onset Status of Adverse Drug Reactions or Infections by Presence or Absence of Bleeding-related Event Complications

Statistical Analysis Set	Safety-evaluable patients in this special drug use surveillance
Details of Statistical Analysis	Compile ADR types by presence or absence of bleeding-related event complications. The compilation method of ADR types is the same as described in section 2.4.1.
Figure/Table No.	Table 2.4.19

2.4.20 Onset Status of Adverse Drug Reactions or Infections by Presence or Absence of Concomitant Anticoagulant and/or Antiplatelet Drugs

Statistical Analysis Set	Safety-evaluable patients in this special drug use surveillance
Details of Statistical Analysis	Compile ADR types by presence or absence of concomitant anticoagulant or antiplatelet drugs (Concomitant anticoagulant / antiplatelet , Anticoagulant only, Antiplatelet only, Neither). The compilation method of ADR types is the same as described in section 2.4.1.
Figure/Table No.	Table 2.4.20

2.4.21 Onset Status of Adverse Drug Reactions (Bleeding-Related Events) by Presence or Absence of Concomitant Anticoagulant and/or Antiplatelet Drugs

Statistical Analysis Set	Safety-evaluable patients in this special drug use surveillance
Details of Statistical Analysis	Compile the types of adverse drug reactions (bleeding-related events) by presence or absence of concomitant anticoagulant or antiplatelet drugs (Concomitant anticoagulant / antiplatelet , Anticoagulant only, Antiplatelet only, Neither). The compilation method of the types of adverse drug reactions is the same as described in section 2.4.1.
Figure/Table No.	Table 2.4.21

2.4.22 Onset Status of Adverse Drug Reactions or Infections by Baseline Fasting Triglyceride Level

Statistical Analysis Set	Safety-evaluable patients in this special drug use surveillance whose fasting triglyceride levels were measured at baseline

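### Protocol Table 3 lets one event qualify as both Related and Not related, and the row chosen decides whether a bleed enters the SAP's bleeding tables

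*Protocol*

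**What the plan says.** Protocol 9.6, Table 3, offers three causality determinations. The first two each consist of two alternatives joined by 'Or'.

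- *Related*, first limb: "There is temporal correlation between the Drug and the event (including results from discontinuation of treatment"). Second limb: an event "considered likely to have been caused by the Drug although it is presumed to have been contributed by other factors", with concomitant medications among the examples.
- *Not related*, first limb: no temporal correlation. Second limb: "Or the event is adequately considered to have been contributed by other factors, such as primary disease, complications, concomitant medications, or combined treatments".
- *Unevaluable*: the information needed for a judgement is lacking.

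A footnote to the survey items in 9.6 says that, for an event judged not related, "reasons that may constitute the rationale for determination should be collected if it is unevaluable".

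SAP 1.1 defines an ADR by exclusion: "Refers to an adverse event other than those judged by the investigator as" not related. Two SAP tables are specific to bleeding. Table 2.4.7 covers bleeding ADRs by seriousness, onset time and outcome. For Table 2.4.21 the instruction is: "Compile the types of adverse drug reactions (bleeding-related events) by presence or absence of concomitant anticoagulant or antiplatelet drugs", in four strata (both, anticoagulant only, antiplatelet only, neither).

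Bleeding is the priority survey item (Protocol 9.6). Protocol 3.2 cites a bleeding-ADR incidence of 0.4% and about 10% antithrombotic use in support of 3,000 patients, and says that this rationale is not statistical.

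**The concern.** A causality table should send each assessable event to one row. Here a bleed whose timing fits the Drug, in a patient who also takes an anticoagulant, can properly be put in either of two rows. Two investigators who follow the table faithfully can therefore disagree, and under the SAP's ADR definition one of them removes the event from every ADR table.

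What is at stake is the comparison that Protocol 3.2 gives as part of the reason for the sample size: bleeding ADRs with and without antithrombotic co-medication. An antithrombotic is a ready contributor of a kind that Table 3 itself lists, so it is plausible that users' bleeds leave the count at a different rate from non-users' bleeds. The footnote that should record why an event was called *Not related* does not clearly require it.

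**Working it through.** **1. The rows side by side.** Take an event with temporal correlation and another credible contributor.

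| Test | Met? |
|---|---|
| *Related*, limb 1: temporal correlation | Yes, sufficient alone |
| *Related*, limb 2: Drug likely causal despite other factors | Possibly |
| *Not related*, limb 1: no temporal correlation | No, but not required because of the 'Or' |
| *Not related*, limb 2: other factors adequately contributed | Yes, if the contributor is credible |

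The second limbs of both rows list the same kinds of factor, so the presence of a co-contributor does not separate them.

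**2. Search for a tie-break.** Table 3 has none. SAP 2.4.6 ranks Related, then Unevaluable, then Not related, but for adverse events that occur more than once in one patient. SAP 2.4.37 counts a patient as related when the same preferred term occurs with both judgements. Both rules handle several events in one patient, not one event that fits two rows.

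**3. Where the choice acts.** Tables 2.4.7 and 2.4.21 contain ADRs only. The all-causality tables, 2.4.3 and 2.4.6, are by system organ class and preferred term, with no bleeding grouping and no antithrombotic strata.

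**4. The footnote.** *Not related* and *Unevaluable* are separate determinations in Table 3. A rationale for the first that is conditional on the second has no consistent reading.

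**5. Expected counts.** The target of 3,000 has no formula to reproduce. The protocol's figures imply:

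- bleeding ADRs: 3,000 × 0.004 = 12
- antithrombotic users: 3,000 × 0.10 = 300; non-users 2,700
- at equal rates: 300 × 0.004 = 1.2 in users and 2,700 × 0.004 = 10.8 in non-users
- chance of none in users: (1 − 0.004)^300 = 0.30

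The 1.2 is shared among the three exposed strata of Table 2.4.21.

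**6. Effect of re-classing a few user bleeds.** The splits of 12 events below are assumptions. The ratio is (users' bleeds/300) ÷ (non-users' bleeds/2,700).

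| Split (users/non-users) | Ratio | One user bleed re-classed | Two re-classed |
|---|---|---|---|
| 1/11 | 0.82 | 0 | – |
| 2/10 | 1.8 | 0.9 | 0 |
| 3/9 | 3.0 | 2.0 | 1.0 |

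**7. When the ratio is biased.** If R is the true ratio, and q1 and q0 are the shares of temporally correlated bleeds called *Not related* in users and non-users, the counted ratio is R × (1 − q1)/(1 − q0). The documents give none of these values. With R = 3:

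- q1 = 25%, 50% or 75% and q0 = 0: 2.25, 1.5 or 0.75
- q1 = q0 = 25%: 3 × 0.75/0.75 = 3.0, unchanged
- q1 = 0, q0 = 1/3: 3 ÷ (2/3) = 4.5, biased the other way

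**The case against.** The strongest reply is that *Related* has a second limb written for this case: a likely drug effect remains *Related* even when a co-medication contributed. Read together, the second limbs ask for a judgement, and the word 'adequately' sets some threshold for *Not related*. That is fair, but no rule is given for weighing the Drug against the other factor, and limb 1 of *Related* is still met by timing alone. The overlap stands.

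A reader might infer three stronger things that the documents do not support.

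- *Any bleed on treatment meets Related.* Temporal correlation is not defined, and the table links it to what happens on discontinuation. Being on the Drug need not be enough.
- *The plan removes bleeds differentially from users and so hides an interaction.* Non-users can also have a listed contributor, such as a complication or the primary disease. Investigators alert to the priority item might lean towards *Related* in users. Step 7 shows that the ratio can fall, rise or stay the same.
- *A Not related call cannot be checked afterwards.* All adverse events are tabulated by preferred term and by causality, serious events with causality denied appear in brackets (SAP 2.4.37), bleeding-related laboratory values and co-medications are collected, and the sponsor may request a re-survey (Protocol 7.4). What is missing is a clearly required rationale and a bleeding table that ignores causality.

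Two limits on the numbers also stand. The 0.4% is an ADR rate, so it already follows a causality judgement, and using 12 as the count before re-classing is only a scale. The estimates are also imprecise: for 3/300 against 9/2,700 the conditional exact 95% interval for the ratio is about 0.5 to 12, and the shifts to 2.0 and 1.0 lie inside it. The current SAP plans no test of this comparison.

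**Conclusion.** The concern holds as a defect of a stated rule: Table 3 is not mutually exclusive, nothing downstream resolves the overlap, and the row chosen decides whether a bleed enters Tables 2.4.7 and 2.4.21. The footnote is self-contradictory. These conclusions rest on the text alone.

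The consequence for the antithrombotic comparison is a possibility of unknown size and direction. It requires that users and non-users have different shares of temporally correlated bleeds called *Not related*. What can be said is that the counts are small enough (about 12 overall, about 1.2 in users at equal rates) for one or two judgements to change the users' result. The ratios in step 6 depend on the assumed splits and on 0.4% and 10% carrying over to this population.

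**What to change.** 1. **Make the rows exclusive.** *Not related* should apply only if there is no temporal correlation, or if other factors explain the event and the Drug is considered unlikely to have contributed. Any other assessable event is *Related*; *Unevaluable* stays for missing information. The protocol's First Version had a gloss of this kind on the *Not related* row: "if the Drug is considered unlikely to have contributed to the event". That text is superseded and is cited only as ready wording.
2. **Correct the footnote.** Collect a rationale for each *Not related* call and, separately, the reason for each *Unevaluable* call.
3. **Add one SAP table.** Show bleeding-related adverse events (SMQ 20000038, narrow scope) regardless of causality, by the four strata of 2.4.21. The surveillance period in Protocol 8.0 ended on May 31, 2017, so new wording may not reach judgements already made. This table does not depend on those judgements.

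The cost is a few sentences in the protocol, one table from data already collected, and slightly more events counted as ADRs.
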